## II Follow-up questionnaire

	LOGO FIELD ORGANIZAT	ION					ZEG	
				INAS-VIPOS				
			- Follow-	up Questionnaire l	No. [N] –			
					بينال			
If voi	ı have any questions, pleas	e call our fre	ee phone numbe	Count	ry Physician	no. Patient r	no. ID	
_	ometriosis Treatment	o our our m	oc priorio riamo	or. [terepriene namber]				
1.	Have you used any ho	ormonal tr	eatment for y	our endometriosis since	we last heard	from you in [mo	onth/year]?₁	
	☐ Yes → Please fill in a	all medicatio	ns with dates a	nd reasons for stopping / switc	1			e below
Brar	nd name of medication 2	F	rom	То	(Please tick appro		ng	
		month 3	year 4	ongoing 7	☐ Trying to beco☐ Treatment dur☐ Medication ine☐ Side-effects of☐ Which:	ration finished effective f medication		9
		M M L	Y Y Y Y Y year	month year ongoing	Other (e.g. sympto	ome pregnant ration finished effective f medication		10
		M M L	Y 1 Y 1 Y 1 Y 1	W_M   Y_Y_Y_Y   Wear   ongoing	Other (e.g. symptotics) Trying to become treatment dure Medication ine Side-effects of Which: Other (e.g. symptotics)	ome pregnant ration finished effective f medication		
		M_M_L	Y I Y I Y I Y I Y I Y I	month year ongoing	☐ Trying to beco☐ Treatment dur☐ Medication ine☐ Side-effects of Which:	ome pregnant ration finished effective f medication		
					Other (e.g. sympto			
	
 
No, I have not use [month/year] until the provide the medication(s) by
 
	today. e reason fo	r not using the p		☐ Trying to beco ☐ Treatment dur ☐ Medication ine ☐ Side-effects of Which:	ration finished effective f medication		
2.	Since we last heard fro	m vou in	[month/year]	, have you had surgery/la	Other (e.g. sympto		ndometrics	
	□ No → Go to ques If yes, please specify to	tion 3 he type an	☐ Yes Id date of surg	ery (if known) in the table lery, diagnostic laparoscop	below (i.e. excis	ion of lesions, re	emoval of ova	
	Operation 12					Date		
						M_M_13_Y_Y month 13 y	year 14	
						M_M Y_Y	year	
Medi 3.	cal History  We last heard from yo	u in [mon	th/year]. Sind	ce then, have you had an	v of the followi	ng diseases?		
Ane	emia 15	□ No	☐ Yes, dia		Y Y Y Y Y 17			
7			I was	treated by a physician 66 treated with iron tablets 18	year 17	□ Yes	□ No	
				treated with an iron infusion	Lan	□ Yes	□ No □ No	
				treated with a blood transfus		□ Yes	□ No	
				r treatment?. 21		□ Yes	□ No	
			If yes	, which?				_ 22
	p venous thrombosis	□ No	☐ Yes, in	month 24	year 25			
	Pulmonary embolism 23 ad clot in the deep veins e.g.	3	I was	treated by a physician 26	,	□ Yes	□ No	
	arms or blood clots in the lung)		I was	treated with blood-thinning	drugs 27	□ Yes	□ No	
			If yes	s which drugs?				28
				 				

Supporting document SOP BMT 01.09 – Doc 5002.02 – Effective date 21.03.2017

Dep	ression requiring	□ No	☐ Yes, diagn	osed in	M 30 Y Y Y	31		
treatment 29				eated by a gener	al practitioner 32		Yes	□ No
			l .	eated by a psych Imitted to hospita			∃ Yes ∃ Yes	□ No □ No
			l	ed Suicide 35	11 34		Yes	□ No
Oth	er serious diseases /	□ No	☐ Yes, which					
ope	rations 36		1		37	When?	M M 38 Y	Y . Y . Y J
	gynecological diseases, rtension, diabetes and cancer)		l was	treated by a phy	sician 40		Yes	□ No
			2			When?	MMIY	Y , Y , Y .
			l was	treated by a phy	sician		M_M LY_ month Yes	year □ No
Modi	cations		If you have	had more than 2 seriou	s diseases/operations, p	lease use the	comment field.	
4.	Are you taking any oth	er medica	tion on a requ	lar basis? (NOT	including the med	tication(s)	listed in guestion	1)
-		er medica	don on a regu		one(s)? (please			-
				L 103, Willott	one(s): (picase	aso brain	a name ii knewi	''
	14-1141							42
	oitalization	ماناها هامانده	mr have ver	been admitted	to a boonital (fo	r of loop	t ana niaht) sir	
oa.	With the exception of c [month/year]? 43	iniia aeiive	ery, nave you	been admitted				
	□ No → Go to ques	stion 6		☐ Yes	When	was it?	month 44	year 45
	If yes, was the hosp  ☐ No	oital stay pl	anned? 46	□ Yes				
5b.	What was the reason for	or this hos	pital stay? (PI		ic as possible)			
					. ,			47
50	Was an operation perfo	ormed?						47
36.		Jilleu : 48		□Yes	When	was it?	M M 49	Y . Y . Y I
				L 103	WITCH	was it:	month 49	year 50
	it ves inlease specif	fy the type	of operation:					
Weig	If yes, please specif	fy the type	of operation:					. 51
Weig								
6.	ht	fy the type						51
6. Preg	ht What is your weight?	 	kg					51
6. Preg	ht What is your weight? nancy Have you had a baby s	ince [mon	kg	□ Yes W	hen was the deli	iverv? I	D,D][M,M]	51
6. Preg 7a.	what is your weight?  nancy  Have you had a baby s  □ No → Go to ques	ince [mon	Lighth/year]? 53				day s4 M , M	51 55 Year 56
6. Preg 7a.	what is your weight?  nancy  Have you had a baby s  □ No → Go to ques  Have there been any se	ince [mon	Lighth/year]? 53	problems with t			D_D_S4 M_M_M day 54 month	51 55 year 56
6. Preg 7a.	what is your weight?  nancy  Have you had a baby s  □ No → Go to ques  □ No	ince [mon stion 8a erious hea	th/year]? 53				D D S4 M M M day 54 month	
6. Preg 7a. 7b.	what is your weight?  nancy  Have you had a baby si  □ No → Go to quest  Have there been any se  □ No  If yes, please specif	ince [mon stion 8a erious hea	th/year]? 53	problems with t			D D S4 M M M day 54 month	51  51  52  53  54  55  55  56  56
6. Preg 7a. 7b.	what is your weight?  nancy  Have you had a baby s  □ No → Go to ques  Have there been any se □ No □ No □ If yes, please specif	ince [mon stion 8a erious hea	th/year]? 53  Ith issues or p	oroblems with t ☐ Yes	the newborn? 57			58
6. Preg 7a. 7b.	what is your weight?  nancy  Have you had a baby s  □ No → Go to quest  □ No □ No □ If yes, please specificate are interested in the imp	ince [mon stion 8a erious hea	th/year]? 53  Ith issues or problems:	Yes	the newborn? 57	ı your mo	ood and wheth	er this changes
6. Preg 7a. 7b. Mood We ove	what is your weight?  nancy  Have you had a baby si  □ No → Go to quest  Have there been any se □ No □ fyes, please specified  are interested in the improve the course of the study	ince [mon stion 8a erious hea	th/year]? 53  Ith issues or problems:	roblems with to ☐ Yes	the newborn? 57	ı your mo	ood and wheth	er this changes
6. Preg 7a. 7b. Mood We ove	What is your weight?  nancy  Have you had a baby s  □ No → Go to ques  □ No □ No □ If yes, please specificate are interested in the improvement of the study.  Have you been feeling	ince [mon stion 8a erious hea fy the types pact of end y. Please down, dep	th/year]? 53  Ith issues or page of problems:  Idometriosis all answer these pressed or hope	Yes  dendometrios questions base peless? 59	sis treatment or	ı your mo ve felt ov	ood and wheth er the last 4 w	er this changes
6. Preg 7a. 7b.  Mood We ove 8a.	What is your weight?  nancy  Have you had a baby si  □ No → Go to quest □ No □ No □ If yes, please specificat  are interested in the improvement of the study Have you been feeling □ Never	ince [mon stion 8a erious hear fy the types pact of endy. Please down, dep	th/year]? 53  Ith issues or problems:  Ith issues or problems:  Ith issues or problems:	oroblems with to Yes	sis treatment or ed on how you'	ı your move felt ov	ood and wheth er the last 4 w □ Alway	er this changes
6. Preg 7a. 7b.  Mood We ove 8a.	What is your weight?  nancy  Have you had a baby s  □ No → Go to ques  □ No □ No □ If yes, please specificate are interested in the improvement of the study.  Have you been feeling	ince [mon stion 8a erious hear fy the types pact of endy. Please down, dep	th/year]? 53  Ith issues or particular in the second of problems:  Ith issues or particular in the second of problems in the second of problems in the second of particular in the second of particula	oroblems with to Yes	sis treatment or ed on how you'	ı your move felt ov	ood and wheth er the last 4 w □ Alway	er this changes
6. Preg 7a. 7b.  Mood We ove 8a.	What is your weight?  nancy  Have you had a baby si  □ No → Go to quest □ No □ No □ If yes, please specificat  are interested in the improvement of the study Have you been feeling □ Never	ince [mon stion 8a erious hear fy the types pact of endy. Please down, dep	th/year]? 53  Ith issues or particles of problems:  Idometriosis alanswer these pressed or hopely  The a failure an	oroblems with to Yes	sis treatment or ed on how you'	your move felt over ten	ood and wheth er the last 4 w □ Alway	er this changes eeks.
6. Preg 7a. 7b. Mooo We ove 8a. 8b.	What is your weight?  nancy  Have you had a baby s  □ No → Go to quest  Have there been any se □ No If yes, please specificate  are interested in the imprime the course of the study  Have you been feeling □ Never  Have you been feeling	ince [mon stion 8a erious hear fy the types oact of endy. Please down, dep	th/year]? 53  Ith issues or particles of problems:  Ith issues or particles are answer these pressed or hopely are a failure and the state of the st	oroblems with to Yes  Ind endometrios questions base peless? 59  Sometimes d have let down	sis treatment or ed on how you'd	your move felt over ten	ood and wheth er the last 4 w □ Alway nily? ₅₀	er this changes eeks.
6. Preg 7a. 7b. Mooo We ove 8a. 8b.	What is your weight?  nancy  Have you had a baby s  □ No → Go to quest  □ No □ If yes, please specificate  are interested in the improvement of the study.  Have you been feeling □ Never  Have you been feeling □ Never	ince [mon stion 8a erious hear fy the types oact of endy. Please down, dep	th/year]? 53  Ith issues or passed of problems:  Idometriosis alanswer these pressed or hopely  The a failure analy  Each about the fut	oroblems with to Yes  Ind endometrios questions base peless? 59  Sometimes d have let down	sis treatment or ed on how you'd	your move felt ov ten nd/or far	ood and wheth er the last 4 w □ Alway nily? ₅₀	er this changes eeks.
6. Preg 7a. 7b. Mooo We ove 8a. 8b.	What is your weight?  nancy  Have you had a baby s  □ No → Go to quest  Have there been any se □ No □ If yes, please specificat  are interested in the imprice the course of the study Have you been feeling □ Never  Have you been feeling □ Never  Have you felt happy or	ince [mon stion 8a erious hear fy the types oact of endy. Please down, dep like you are represented as Rare	th/year]? 53  Ith issues or problems:  Ith iss	oroblems with to Yes  Ind endometrios questions base peless? 59  Sometimes d have let down Sometimes cure? 61  Sometimes	sis treatment or ed on how you'  Of n your friends a	your move felt ov ten nd/or far	ood and wheth rer the last 4 w □ Alway nil y? ₅₀ □ Alway	er this changes eeks.
6. Preg 7a. 7b. Mood We ove 8a. 8b.	What is your weight?  nancy  Have you had a baby s  □ No → Go to quest  Have there been any se □ No □ If yes, please specificat  are interested in the impriment of the study.  Have you been feeling □ Never  Have you been feeling □ Never  Have you felt happy or □ Never	ince [mon stion 8a erious hear fy the types oact of endy. Please down, dep like you are represented as Rare	th/year]? 53  Ith issues or passed of problems:  Idometriosis alanswer these pressed or hopely  The a failure analy  Each about the fut	oroblems with to Yes  Independent of the Yes	sis treatment or ed on how you'  Of n your friends a	your move felt ov ten nd/or far	ood and wheth rer the last 4 w □ Alway nil y? ₅₀ □ Alway	er this changes eeks.
6. Preg 7a. 7b. Mood We ove 8a. 8b.	What is your weight?  nancy  Have you had a baby si  □ No → Go to quest □ No □ If yes, please specified  are interested in the imprime the course of the study Have you been feeling □ Never  Have you been feeling □ Never  Have you felt happy or □ Never  Please fill in today's dament	ince [mon stion 8a erious hear fy the types oact of endy. Please down, dep Rare optimistic Rare	th/year]? 53  Ith issues or problems:  Ith iss	oroblems with to Yes  Independent of the Yes	sis treatment or ed on how you'  Of n your friends a	your move felt ov ten nd/or far	ood and wheth rer the last 4 w □ Alway nil y? ₅₀ □ Alway	er this changes eeks.
6. Preg 7a. 7b. Mood We ove 8a. 8b. 8c.	What is your weight?  nancy  Have you had a baby s  □ No → Go to quest  Have there been any se □ No □ If yes, please specificat  are interested in the impriment of the study.  Have you been feeling □ Never  Have you been feeling □ Never  Have you felt happy or □ Never	ince [mon stion 8a erious hear fy the types oact of endy. Please down, dep Rare optimistic Rare	th/year]? 53  Ith issues or problems:  Ith iss	oroblems with to Yes  Independent of the Yes	sis treatment or ed on how you'  Of n your friends a	your move felt ov ten nd/or far	ood and wheth rer the last 4 w □ Alway nil y? ₅₀ □ Alway	er this changes eeks.

Thank you for your help with this study!

2

F4

Supporting document SOP BMT 01.09 – Doc 5002.02 – Effective date 21.03.2017

## III List of potential prognostic factors for primary outcomes

Primary Outcome	Predefined Potential Prognostic Factors
Anemia	EMT user type at follow-up, age, history of anemia, history of bleeding disorders
Depression	EMT user type at follow-up, age, family and personal history of depression, use of Antidepressants/SSRI, severity of pain
Treatment Failure	EMT user type at follow-up, age, family and personal history of depression, current/worsening depression, severity of pain

Supporting document SOP BMT 01.09 – Doc 5002.02 – Effective date 21.03.2017

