A well-known class effect of progestogens is the induction of bleeding disturbances. 72% of women reported inter-menstrual spotting or bleeding as a side-effect of DNG use in a 52-week open-label study in Japan [9]. Metorrhagia symptoms tended to decrease towards the end of this trial and consequently it is not known what influence DNG will have on bleeding disturbances associated with endometriosis over a longer

³ Sentence was added on request of the MEB (revised study protocol of February 28, 2011)

time frame. Given the initial increased incidence of metorrhagia in the Japan study and the overall increased risk of menorrhagia in women with endometriosis, a study assessing the incidence of anemia induced by bleeding disturbances in women receiving medical treatment for endometriosis is needed.

An ongoing concern associated with progestogens has been their potential role in influencing mood disturbances and, in particular, exacerbating depressive symptoms. In 2004, the European Health Authorities requested a desk review of newly diagnosed depression cases from the EURAS-OC study and found no increased risk for women using oral contraceptives compared to non-users [10]. Despite this reassurance, concerns remain. In addition, women who suffer from endometriosis are at high risk of developing depressive symptoms. Sepulcri et al assessed depressive symptoms amongst women with a surgical diagnosis of endometriosis and found 86.5% met SF-36 diagnostic criteria for depression, with 32.7% of women meeting the criteria for a severe depressive disorder [11]. Depressive symptoms may be correlated with the degree of chronic pelvic pain associated with the disease. Lorençatto C, found depressive symptoms in 86% of women with chronic pelvic pain associated with endometriosis while only 38% of women without pelvic pain met the diagnostic criteria for depression [12]. The complexities and potential interaction between depression, endometriosis and progestogens make it difficult to differentiate whether an individual's depressive symptoms are causally associated with progestin use or sequela of the disease process. Consequently, a population-based postauthorization safety study is needed to assess the potential influence of DNG on mood disturbance and depression in endometriosis patients.

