Crude as well as adjusted hazard ratios will be calculated. The appropriate confounding variables will be built into the statistical model. Based on the expectation of a small absolute number of serious outcomes of interest the number of confounding variables will be limited to established risk factors for these outcomes. For anemia these will include age, duration of current use, and family history of bleeding disorders and a past history of anemia. For depression, age, chronic pelvic pain, anxiety disorder and a family history of depression are proposed. For 'treatment failure' chronic pelvic pain, age and previous surgical treatment will be included. The final decision on and the addition of other confounding variables (e.g. country) will be made by the Safety Monitoring and Advisory Council before the first interim analysis of follow-up data. In addition, alternative analysis will be performed with other potential baseline risks to check the appropriateness of this decision.

A detailed statistical analysis plan will be developed by the Principal Investigator during the first year after study start. The final analysis plan will be approved by the Safety Monitoring and Advisory Council before the first interim analysis of follow-up data.

Biannual interim reports will be provided to the funder following release of the interim analyses results by the independent Safety Monitoring and Advisory Council (cf. section 13).

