#### 5.4.2 Regression models

Regression analysis will be performed if a sufficient number of confirmed events are available for estimation, i.e. n≥5 confirmed events in each of the comparison groups.

Potential confounders such as

- age, personal and family history of depression, history of anemia, history of bleeding disorders and severity of pain will be included as time-invariant cofactors.
- EMT user type at follow up, use of Antidepressants/SSRI and current or worsening depression (primary outcome) will be included as time-dependent cofactors.

For each primary outcome, a summary table with predefined potential prognostic factors and the corresponding relative risk estimators is provided.

The final decision on the confounding variables will be made by the Safety Monitoring and Advisory Council:

Primary outcome variable	Predefined Prognostic Factors 	
Anemia	Age, history of anemia, history of bleeding disorders	
Depression	Age, family and personal history of depression, use of Antidepressants/SSRI	
Treatment Failure	Age, family and personal history of depression, severity of pain	

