#### 5.4.2.1 Cox Proportional Hazard Model

Time-to-event (survival) analyses will be undertaken using Cox proportional hazard models (Cox model) to describe how the hazard increases for each unit increase of the regressor variables. Crude and adjusted hazard ratios (HR) comparing subpopulations under study will be calculated for all primary outcomes and 95% HR confidence limits (Wald) are provided. The crude model refers to a univariable model which includes exposure as the only explanatory factor. Potential predefined event-specific prognostic factors (section 5.4.2) are included in multiple models. In the Cox model, recurrent events are included.

18

 See Appendix III for all potential prognostic factors for each primary and secondary outcome.

Supporting document SOP BMT 01.09 – Doc 5002.02 – Effective date 21.03.2017

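### SAP 5.4.2 does not settle whether the depression hazard ratio is adjusted for pain, which Appendix III and the protocol both list

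*SAP*

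**What the plan says.** Five places bear on the covariates for the depression model.

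- **SAP 5.4.2, bullet above the table.** It ends: "history of bleeding disorders and severity of pain will be included as time-invariant cofactors". No outcome is named.
- **SAP 5.4.2, table.** The depression row reads "Age, family and personal history of depression, use of Antidepressants/SSRI". The treatment failure row reads "Age, family and personal history of depression, severity of pain". Pain is in the second and not in the first.
- **SAP 5.4.2.1.** "Potential predefined event-specific prognostic factors (section 5.4.2) are included in multiple models". This makes 5.4.2 the source for the adjusted Cox model. Footnote 10, attached to the table heading, adds: "See Appendix III for all potential prognostic factors for each primary and secondary outcome".
- **SAP Appendix III.** The depression row closes with "use of Antidepressants/SSRI, severity of pain". It also adds endometriosis treatment user type at follow-up.
- **Protocol section 11.** "For depression, age, chronic pelvic pain, anxiety disorder and a family history of depression are proposed".

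The protocol introduction gives the reason for interest in pain: one cited study "found depressive symptoms in 86% of women with chronic pelvic pain associated with endometriosis while only 38% of women without pelvic pain" met the criteria for depression. SAP 5.4.2 leaves the last word on covariates to the SMAC.

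**The concern.** The study is not randomised, and the prescribing physician chooses the drug. The depression hazard ratio for DNG versus OAED is compared with a non-inferiority margin of 2, so the covariate set is part of the test. Pain is a risk factor that the protocol itself proposes for this outcome and supports with a cited contrast. If pain also differs between the two cohorts, leaving it out moves the hazard ratio. It moves down, towards a false finding of non-inferiority, if pain is less common on DNG, and up, with loss of power, if it is more common.

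As written, two analysts could each follow 5.4.2 and fit different adjusted depression models, one with pain and one without. The plan does not say which of the two estimates is the one to compare with the margin.

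**Working it through.** **1. Which list applies?**

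| Source | Pain listed for depression? |
|---|---|
| SAP 5.4.2, bullet | Yes, but no outcome named |
| SAP 5.4.2, table | No (given only to treatment failure) |
| SAP Appendix III | Yes |
| Protocol section 11 | Yes, as chronic pelvic pain |

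The only covariate footnote in the Section D mock tables is for anemia (Table D-1.1.2). It names age, history of bleeding and history of anemia. That is the 5.4.2 table row; Appendix III would add user type. By analogy, the depression row of the 5.4.2 table is the likelier working list. Section D-2 on depression gives table titles only, so it does not decide the matter.

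**2. The plan's own figure.** SAP Table 3 requires 8,400 + 4,200 = 12,600 women-years. At 0.01 per year that is 126 events. The Schoenfeld formula with margin 2, 2:1 allocation, one-sided alpha 0.0083 and 90% power gives

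(2.394 + 1.282)² / [(2/3)(1/3)(ln 2)²] = 13.51 / 0.1068, which rounds up to 127 events, or 12,700 women-years.

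This agrees with Table 3 to within 1%. Adding a covariate does not change the figure; it is used below only to set the precision.

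**3. Strength of the cited association.** Risk ratio = 0.86 / 0.38 = 2.26.

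**4. Bias factor for a crude hazard ratio.** With pain prevalence p1 in DNG and p0 in OAED,

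B = [1 + p1(2.26 − 1)] / [1 + p0(2.26 − 1)].

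Two assumptions are needed. The cited prevalence ratio must carry over to incidence, and prevalences by cohort must be supposed, because the documents give none. For 40% versus 60%, B = 1.505 / 1.758 = 0.856.

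**5. Consequence at 126 events.** Standard error of the log hazard ratio = 1/√(126 × 2/9) = 0.189. The probability of concluding non-inferiority is Φ{[ln 2 − ln(HR × B)]/0.189 − 2.394}.

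| Pain, DNG / OAED (assumed) | B | True HR 2.0 appears as | P(non-inferior) at true HR 2 | Power at true HR 1 |
|---|---|---|---|---|
| 40% / 60% | 0.856 | 1.71 | 0.058 | 0.98 |
| 40% / 50% | 0.923 | 1.85 | 0.025 | 0.96 |
| Equal | 1 | 2.00 | 0.0083 | 0.90 |
| 50% / 40% | 1.084 | 2.17 | 0.002 | 0.80 |
| 60% / 40% | 1.168 | 2.34 | 0.0007 | 0.68 |

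**6. After the planned adjustment.** The table above describes a model with no covariates. The 5.4.2 row already adjusts for depression history and antidepressant use, which may carry part of the pain association. If the remaining risk ratio for pain were 1.3 to 1.5 (an assumption), the 40% / 60% case gives 1.12/1.18 = 0.95 to 1.20/1.30 = 0.92. A true 2.0 would then appear as about 1.90 to 1.85.

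**The case against.** The strongest case on the other side has four parts.

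- **Pain is not simply absent from 5.4.2.** The bullet says it will be included, and 5.4.2.1 refers to the whole section. This stands. A reader might infer from the table alone that the SAP has decided to leave pain out of the depression model. The documents do not support that; they show an unresolved inconsistency.
- **The list is provisional.** The SMAC decides, Appendix III is headed as potential factors, so the 5.4.2 table could be a deliberate subset, and protocol section 11 promises alternative analyses with other baseline risks. This also stands, and it means the gap can still be closed. It does not tell the analyst which list to use for the primary model, and no reason for the shorter one is recorded.
- **The figures are not the bias of the planned model.** The 86% and 38% are cross-sectional, and the protocol words the first as depressive symptoms and the second as diagnostic criteria. The endpoint is new or worsening depression confirmed by a psychiatric specialist, or suicide or attempted suicide. The documents quantify pain's link with depression but not its link with drug choice. A reader might infer that the hazard ratio is biased towards non-inferiority by about 14%. That is not supported: the direction is unknown, and with equal prevalence the bias is nil.
- **Adding pain does not align the lists fully.** Appendix III would still differ on user type. The protocol would still differ on anxiety disorder, which is in neither SAP list, and on the pain measure: chronic pelvic pain rather than a 0 to 10 score over four weeks. This stands.

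**Conclusion.** The inconsistency is certain on the text. SAP 5.4.2 disagrees with itself about pain for depression, and its table row disagrees with Appendix III and with protocol section 11, without explanation. If the row is followed, the hazard ratio tested against 2 is unadjusted for a risk factor the protocol names.

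The size of the resulting bias cannot be known from the documents. The factors of 0.86 and 1.17 for a 20-point imbalance in either direction rest on assumed cohort prevalences, on carrying a prevalence ratio over to incidence, and on a crude model. They illustrate what is possible and do not estimate what will happen. The point should be corrected because the change is cheap and the test depends on the model; it does not show that the depression result would be wrong.

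**What to change.** Add the baseline pain severity score to the depression row of the 5.4.2 table, subject to SMAC confirmation. If the SMAC prefers to leave it out, record the reason and amend the bullet and Appendix III to agree. List the depression covariates in a footnote to the Section D-2 hazard ratio table, as is done for anemia. In the same pass, state whether user type and anxiety disorder are in or out.

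No new data are needed. Every woman is asked for the 0 to 10 score at baseline (question 13), and Appendix IV already derives the three-level version. Because it is recorded at study entry, it is not a consequence of the newly prescribed drug. The cost is one more model term and the handling of women with a missing score. Mock Table B-4.8.1 allows for these, but section 5.5 gives no regression rule for them, so one sentence on that should go in as well.
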